- 3) Section 6.1. Added footnote 13 to T&E calendar about three times weekly labs if patients discharged before early recovery
- 4) Section 6.1 Time and events table. Added buccal swab to be collected at screening. Those patients who did not have buccal swab collected at screening should have this sample collected at any time during follow up (clarified in footnote 12)
- 5) Sections: 6.2., 6.3.3, 6.4.1.1, 6.4.2.1: The following Section were updated to reflect the Thyroid function tests to be done: TSH, T3, and free T4.

The attached version dated November 1, 2017 incorporates the above revisions

PROTOCOL AMENDMENT # 5

LCCC 1522: Phase 2 Study of High Dose Cytarabine Followed by Pembrolizumab in Relapsed and Refractory Acute Myeloid Leukemia

AMENDMENT #5 INCORPORATES (Check all that apply):

- X Editorial
- X Scientific Changes
 - Therapy Changes
 - Eligibility Changes

This protocol is amended to update definition of disease progression for PFS secondary endpoint based on revisions to AML Leukemia Net criteria in 2017. The protocol is revised to include adverse event management language provided in a Dear Investigator Letter issued on 10 February 2017 by Merck and Co., Inc. regarding cases of Stevens-Johnson syndrome (SJS), Toxic Epidermal Necrolysis (TEN) and Immune-mediated myocarditis with pembrolizumab.

Editorial

1. Section 10 Reference #2 revised to include online reference to revised AML criteria in 2017.

Scientific

2. Updated sections 4.4.6 include supportive care guidelines for SJS, TEN and immune-mediated myocarditis.
3. Added SJS, TEN and myocarditis to adverse events associated with pembrolizumab in section 5.1.6
4. Updated section 6.9.1 to include revised definition of disease progression for PFS based on revisions to Leukemia Net criteria for AML in 2017
5. Thyroid Function tests are now required and no longer optional. Thyroid function will be monitored periodically during pembrolizumab maintenance therapy. The following sections were updated to reflect this change, Time and Events table in section 6.1 and footnote #10 to this table, and Sections 6.2, 6.3.3, 6.4.1 and 6.4.2

The attached version dated June 7, 2017 incorporates the above revisions

PROTOCOL AMENDMENT # 4

LCCC 1522: Phase 2 Study of High Dose Cytarabine Followed by Pembrolizumab in Relapsed and Refractory Acute Myeloid Leukemia

AMENDMENT #4 INCORPORATES (Check all that apply):

- X Editorial, Administrative Changes
- X Scientific Changes
- X Therapy Changes

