2.2 Secondary Objectives

- 2.2.1 Estimate the rate of unacceptable toxicity associated with HiDAC followed by pembrolizumab as induction therapy
- 2.2.2 Estimate the objective overall response rates (PR+CR+CRi) for HiDAC followed by pembrolizumab.
- 2.2.3 Characterize the toxicity associated with HiDAC followed by pembrolizumab as induction therapy
- 2.2.4 Characterize the toxicity associated with pembrolizumab 200 mg IV Q3weeks when used as monotherapy maintenance after an initial response to induction phase HiDAC followed by pembrolizumab
- 2.2.5 Estimate the relapse-free survival (RFS) and progression-free survival (PFS) of patients receiving maintenance pembrolizumab
- 2.2.6 Estimate the overall survival (OS) of patients who received induction phase treatment.

[REDACTED]

[REDACTED]

[REDACTED]

[REDACTED]

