- When symptoms improve to Grade 1 or less, steroid taper should be started and continued over no less than 4 weeks.

Type 1 diabetes mellitus (T1DM) (if new onset, including diabetic ketoacidosis [DKA]) or \geq Grade 3 Hyperglycemia, if associated with ketosis (ketonuria) or metabolic acidosis (DKA)

- For **T1DM** or **Grade 3-4 Hyperglycemia**
 - Insulin replacement therapy is recommended for Type I diabetes mellitus and for Grade 3-4 hyperglycemia associated with metabolic acidosis or ketonuria.
 - Evaluate patients with serum glucose and a metabolic panel, urine ketones, glycosylated hemoglobin, and C-peptide.
- **Hypophysitis:**
 - For **Grade 2** events, treat with corticosteroids. When symptoms improve to Grade 1 or less, steroid taper should be started and continued over no less than 4 weeks. Replacement of appropriate hormones may be required as the steroid dose is tapered.
 - For **Grade 3-4** events, treat with an initial dose of IV corticosteroids followed by oral corticosteroids. When symptoms improve to Grade 1 or less, steroid taper should be started and continued over no less than 4 weeks. Replacement of appropriate hormones may be required as the steroid dose is tapered.

Hyperthyroidism or Hypothyroidism:

Thyroid disorders can occur at any time during treatment; monitor patients for changes in thyroid function (at the start of treatment, periodically during

treatment, and as indicated based on clinical evaluation) and for clinical signs and symptoms of thyroid disorders.

Grade 2 hyperthyroidism events (and **Grade 2-4** hypothyroidism):

- In hyperthyroidism, non-selective beta-blockers (e.g. propranolol) are suggested as initial therapy.
- In hypothyroidism, thyroid hormone replacement therapy, with levothyroxine or liothyronine, is indicated per standard of care.

Grade 3-4 hyperthyroidism

- Treat with an initial dose of IV corticosteroid followed by oral corticosteroids. When symptoms improve to Grade 1 or less, steroid taper should be started and continued over no less than 4 weeks. Replacement of appropriate hormones may be required as the steroid dose is tapered.

Hepatic:

- For **Grade 2** events, monitor liver function tests more frequently until returned to baseline values (consider weekly).
 - Treat with IV or oral corticosteroids
- For **Grade 3-4** events, treat with intravenous corticosteroids for 24 to 48 hours.

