Nephritis occurred in 3 (0.7%) patients of melanoma patients treated in clinical trials of pembrolizumab, consisting of one case of Grade 2 autoimmune nephritis (0.2%) and two cases of interstitial nephritis with renal failure (0.5%), one Grade 3 and one Grade 4. The time to onset of autoimmune nephritis was 11.6 months after the first dose of pembrolizumab (5 months after the last dose) and lasted 3.2 months; this patient did not have a biopsy. Acute interstitial nephritis was confirmed by renal biopsy in two patients with Grades 3-4 renal failure. All three patients fully recovered renal function with treatment with high-dose corticosteroids (greater than or equal to 40 mg prednisone or equivalent per day) followed by a corticosteroid taper.

Immune-Mediated Hyperthyroidism

Hyperthyroidism occurred in 5 (1.2%) of 411 melanoma patients treated in clinical trials of pembrolizumab. The median time to onset was 1.5 months and the median duration was 2.8 months (range 0.9 to 6.1). One of two patients with Grade 2 and the one patient with Grade 3 hyperthyroidism required initial treatment with high-dose corticosteroids (greater than or equal to 40 mg prednisone or equivalent per day) followed by a corticosteroid taper. One patient (0.2%) required permanent discontinuation of pembrolizumab due to hyperthyroidism. All five patients with hyperthyroidism experienced complete resolution of the event.

Immune-Mediated Hypothyroidism

Hypothyroidism occurred in 34 (8.3%) of 411 melanoma patients treated in clinical trials of pembrolizumab. The median time to onset of hypothyroidism was 3.5 months. All but two of the patients with hypothyroidism were treated with long-term thyroid hormone replacement therapy. The other two patients only required short-term thyroid hormone replacement therapy. No patient received corticosteroids or discontinued pembrolizumab for management of hypothyroidism. Thyroid disorders can occur at any time during treatment.

Other Immune-Mediated Adverse Reactions

Other clinically important immune-mediated adverse reactions can occur. The following clinically significant, immune-mediated adverse reactions occurred in less than 1% of patients treated with pembrolizumab, including exfoliative dermatitis, uveitis, arthritis, myositis, pancreatitis, hemolytic anemia, partial seizures arising in a patient with inflammatory foci in brain parenchyma, and adrenal insufficiency.

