⁸ Serum chemistries include Na, K, Cl, creatinine, BUN, calcium, magnesium, bicarbonate, and glucose; serum chemistries along with LDH, uric acid, and phosphate comprise tumor lysis labs. During induction, tumor lysis labs should be assessed BID (twice daily) D1-5, and once daily from D6 until tumor lysis syndrome is resolved, which usually occurs by D10. Repeat LDH, uric acid and phosphate on D14.

⁹ Liver function tests (LFTs) include total protein, albumin, total bilirubin, alkaline phosphatase, ALT, and AST (**NOTE:** on D6-13, and on D15 through recovery, LFTs only required every other day); coagulation labs include PT/INR, aPTT, D-Dimer and fibrinogen

¹⁰Thyroid tests include T3, free T4, TSH as denoted during induction therapy. These tests should be performed on D1/C1 prior to starting maintenance therapy with pembrolizumab and repeated every 3 cycles thereafter (i.e., cycles 3, 6, 9, 12, etc.) until treatment discontinuation.

¹¹Initial (pre-treatment) bone marrow biopsy should be obtained within 14 days prior to D1 of HiDAC as per standard of care. Patients will undergo repeat bone marrow at time of full hematologic recovery or on D45 +/- 2 days whichever comes first as per standard of care. Repeat biopsy after every 4 cycles of maintenance during year 1 and every 6 cycles of maintenance during year 1-2. Each time a bone marrow biopsy is done as per standard of care, additional 4x8mL will be collected in green top ACD tubes (~32 mL) for correlative studies. See section 6.7 and the laboratory manual for additional details. Repeat biopsy at any time if there is a suspicion of leukemia recurrence either during maintenance phase or in follow-up.

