6.3.3 Day 14 (Day of Pembrolizumab infusion)

Clinical evaluation: focused history on symptoms/toxicity, physical examination to include weight.

Laboratory studies:

- **Pregnancy Test:** A serum or urine pregnancy test (β -HCG) is required for all women of childbearing potential prior to dose of pembrolizumab. If urine test is positive or cannot be confirmed as negative, a serum pregnancy test will be required.
- **CBC with differential and platelets**
- **Serum Chemistries:** sodium, potassium, chloride, bicarbonate, BUN, serum creatinine, glucose, calcium, magnesium.
- **LFTs: total protein, albumin,** total bilirubin (direct and indirect), alkaline phosphatase, AST (SGOT), ALT (SGPT)
- **Thyroid Function Tests:** TSH, T3, free T4
- **Coagulation Tests:** PT/INR, aPTT, D-Dimer, fibrinogen
- **LDH, Uric acid & phosphate:**

Concomitant Medications: Review (see section 4.4.6)

Toxicity Assessment: via NCI CTCAE v4

Blood sample for Biomarkers: Collect blood sample: see section 6.7 and the laboratory manual for additional details.

6.3.4 Daily (unless otherwise noted) Day 15 until Early Hematologic Recovery or Discharge from Hospital (see footnote #2 for definition)

Laboratory Studies:

- **CBC with differential and platelets**
- **Serum Chemistries:** sodium, potassium, chloride, bicarbonate, BUN, serum creatinine, glucose, calcium, magnesium.
- **LFTs:** total protein, albumin, total bilirubin (direct and indirect), alkaline phosphatase, AST, ALT: **Note: To be drawn every other day**

Blood sample for biomarkers: Collect blood sample weekly between day 14 and hematologic recovery (i.e., day 21, day 28, day 35, day 42 (the latter 2 dates if no hematologic recovery by this time).

- Toxicity Assessment: via NCI CTCAEv4

6.3.5 At Full Hematologic Recovery or on Day 45 +/- 2 days (whichever comes first)

Clinical Evaluation: Physical exam including weight

Laboratory Studies:

- **CBC with differential and platelets**
- **Serum Chemistries:** sodium, potassium, chloride, bicarbonate, BUN, serum creatinine, glucose, calcium, magnesium
- **LFTs:** Total protein, albumin, bilirubin (direct and indirect), alkaline phosphatase, AST, ALT

Toxicity Assessment: via NCI CTCAE v4

Disease Assessment and Biomarkers: Repeat bone marrow biopsy; collect blood sample for biomarkers; see section TBD and laboratory manual for additional details.

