6.8 Assessment of Safety

Any patient who receives pembrolizumab treatment on this protocol will be evaluable for toxicity. Each patient will be assessed periodically for the development of any toxicity according to the Time and Events table (6.0). Toxicity will be assessed according to NCI CTCAE v4. Toxicities will be characterized in terms of seriousness, causality, toxicity grading, and action taken with regard to trial treatment.

For subjects receiving treatment with pembrolizumab, all AEs of unknown etiology associated with pembrolizumab exposure should be evaluated to determine if it is possibly an event of clinical interest (ECI) of a potentially immunologic etiology (termed immune-related adverse events, or irAEs); see the separate ECI guidance document (provided as a document separate from this protocol) regarding the identification, evaluation and management of potential irAEs.

Please refer to section 7.0 for detailed information regarding the assessment and recording of AEs.

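### Pembrolizumab recipients who never start maintenance have no scheduled thyroid test after the drug, and no one has one at end of treatment, so laboratory-only thyroid toxicity is under-ascertained; the expected loss is small and the remedy cheap

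*Combined protocol and SAP*

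**What the plan says.** The table in 6.1, its footnote 10 and sections 6.2 to 6.6 agree on when thyroid function is tested:

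- pre-study (6.2);
- on day 14 (6.3.3), headed "Day 14 (Day of Pembrolizumab infusion", so this test is in effect the baseline for the first dose;
- on maintenance: "These tests should be performed on D1/C1 prior to starting maintenance therapy with pembrolizumab and repeated every 3 cycles thereafter", with cycles 3, 6, 9 and 12 given as examples, until treatment discontinuation.

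No thyroid test is listed from day 15 to recovery (6.3.4), at recovery/D45 (6.3.5), at end of treatment (6.5) or in follow-up (6.6). The recovery/D45 and end-of-treatment visits do include a blood count, chemistries, liver tests and a toxicity assessment.

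On who counts for safety, 6.8 states: "Any patient who receives pembrolizumab treatment on this protocol will be evaluable for toxicity". Section 2.4.2 says the same. Objective 2.2.3 is to "Characterize the toxicity associated with HiDAC followed by pembrolizumab as induction therapy", and 2.2.4 covers maintenance toxicity separately. Section 8.3 plans frequency tables and 95% confidence intervals. It does not say how to report a laboratory event that part of the evaluable set was never scheduled to be tested for.

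**The concern.** A patient can be counted as evaluable for thyroid toxicity without any thyroid measurement after exposure. Who is measured is not random: a scheduled post-dose test requires a response to induction and entry into maintenance. In non-responders a laboratory-only abnormality surfaces only if something else prompts a test.

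Maintenance patients are also affected. Nothing is measured at end of treatment, so changes after the last scheduled test can be missed. A patient who stops before cycle 3 has no scheduled test after any maintenance dose.

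At stake is a descriptive secondary safety result. A low count of thyroid events after induction could be read as evidence of absence when most patients were not tested.

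**Working it through.** **Inputs.** From 8.1: 37 patients; CR/CRi 20% under the null and 40% under the alternative; PR rate 0 to 5% (stated under the null, assumed here for both). From 5.1.6: hypothyroidism 34/411 = 8.3%, where "The median time to onset of hypothyroidism was 3.5 months"; hyperthyroidism 5/411 = 1.2%, median onset 1.5 months. From 7.2: non-serious events are documented to 30 days after treatment stops.

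**The plan's own figures.** The documents give none for thyroid detection. The two-stage design that supplies the response rates does reproduce. By exact calculation over PR 0 to 5%, type 1 error is 0.047 to 0.050 (stated: at most 5%) and power 0.841 to 0.858 (stated: at least 84%).

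**Patients without a scheduled post-dose test** = 37 × (1 − response rate):

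| CR/CRi + PR | Tested, at most | Not tested, at least |
|---|---|---|
| 20% | 7.4 | 29.6 |
| 25% | 9.25 | 27.75 |
| 40% | 14.8 | 22.2 |
| 45% | 16.65 | 20.35 |

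The tested counts are upper bounds. Under 4.3, responders with unacceptable induction toxicity, or who have not started by day 60, do not enter maintenance.

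**Expected cases arising in untested patients.** Assume the melanoma incidence applies and onset is exponential with the stated medians. The fraction with onset by t months is 1 − 0.5^(t/median). For one dose on day 14, the 30-day window closes at about day 44, so t = 1.

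- Hypothyroidism: 1 − 0.5^(1/3.5) = 0.180; 0.0827 × 0.180 = 0.0149 per patient; × 20.35 to 29.6 = 0.30 to 0.44.
- Hyperthyroidism: 1 − 0.5^(1/1.5) = 0.370; 0.0122 × 0.370 = 0.0045 per patient; × 20.35 to 29.6 = 0.09 to 0.13.
- Sum: 0.39 to 0.57 cases, before any credit for symptom-driven detection.

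At t = 2 months the same formulas give per-patient risks of 0.0271 and 0.0073. The sum is then 0.70 to 1.02, but much of that falls outside the non-serious collection window.

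**Maintenance.** Tests fall at cycles 1, 3, 6, …, 33, which is 12 tests over 34 cycles. A patient whose last dose is cycle 5 was last tested on day 1 of cycle 3. With end of treatment about 30 days after the last dose, that visit comes 2 × 21 + 30 = 72 days after the last thyroid test.

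**Why the number tested matters.** With zero events, the exact two-sided 95% upper limit is 1 − 0.025^(1/n): 9.5% for n = 37, 20% for n = 17 and 41% for n = 7.

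**The case against.** The strongest reply has four parts.

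1. The D1/C1 test comes after the induction dose and before any maintenance dose, so every maintenance entrant has a scheduled test reflecting induction exposure alone.
2. Clinical detection covers everyone. Section 4.4.6 asks for thyroid monitoring at the start, periodically during "treatment, and as indicated based on clinical evaluation) and for clinical signs and symptoms of thyroid disorders", and toxicity assessment continues at recovery/D45, end of treatment and follow-up.
3. The protocol's onset medians predict few thyroid events within a month of one dose even with full testing: 37 × 0.0149 = 0.55 hypothyroid and 37 × 0.0045 = 0.17 hyperthyroid cases.
4. Section 8.3 is descriptive, and no thyroid comparison between phases is planned.

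All four stand, and they limit the point. A reader might infer that induction thyroid toxicity is near zero by design and must rise with maintenance by construction. The documents do not support that: parts 1 and 2 provide detection, and late onset and longer exposure would also raise a maintenance rate.

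A reader might also infer that a true 8.3% would be reported as 1.7% to 3.7% (8.3% × 0.20 to 0.45). That requires the full melanoma incidence after a single dose, no clinical detection and a pooled thyroid rate that is not planned. If clinical work-up found half of the untested cases, the same sum gives 5.0% to 6.0%.

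Nor can anything be sized from the Amendment 5 log entry, "Thyroid Function tests are now required and no longer optional". The documents do not say how many patients preceded it or whether they went untested.

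What the reply does not answer is that D1/C1 reaches only patients who enter maintenance, and that symptom-driven testing does not find laboratory-only change.

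**Conclusion.** The gap is real and modest. About 20 to 30 of 37 evaluable patients have no scheduled thyroid test after pembrolizumab, and maintenance patients have none at end of treatment. Laboratory-only thyroid toxicity after the induction dose is therefore under-ascertained, and scheduled detection depends on response.

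The expected loss is roughly half a case among untested patients within about a month of the dose, and less to the extent that clinical work-up finds cases. This rests on exponential onset and on transferring melanoma rates to AML patients given one dose. All 34 hypothyroid patients in 5.1.6 received hormone replacement, so those rates may not capture laboratory-only change; the documents give no figure for it.

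The primary endpoint is unaffected. The boundary in 8.2 counts drug-related non-hematologic grade 3 toxicity lasting more than 7 days, or grade 4-5, so it probably changes little.

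**What to change.** - In 6.1 (table and footnote 10), 6.3.5 and 6.5, add the existing panel (TSH, T3, free T4) to the blood already drawn at recovery/D45 and at end of treatment. For a one-dose patient, end of treatment falls near day 14 + 30 = 44, so one test suffices where the two visits coincide.
- In 6.8 or 8.3, report thyroid events over all treated patients and show beside each rate the number with at least one post-dose thyroid test. A tested-only denominator should not be the sole analysis: for induction it would consist of responders who reached maintenance plus patients tested because of symptoms.
- State that abnormalities on the pre-dose D1/C1 test are reported under induction; the plan does not now say.

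The cost is one or two added assays per patient, two schedule entries and two sentences of analysis text. The thyroid rate may look less favourable. For one-dose patients the added tests cover only about the first month after the dose, so later onset would still depend on clinical detection.

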6.2 Pre-Study Assessments

Clinical evaluation: complete history, physical examination to include height (baseline only) and weight, ECOG performance status.

Transthoracic Echocardiogram

Laboratory studies:

- **Pregnancy Test:** A serum or urine pregnancy test (β -HCG) is required for all women of childbearing potential at screening within 72 hours prior to the first dose of HiDAC. If urine test is positive or cannot be confirmed as negative, a serum pregnancy test will be required.
- **CBC with differential and platelets**
- **Serum Chemistries:** These include the following parameters: sodium, potassium, chloride, bicarbonate, BUN, serum creatinine, glucose, calcium, and magnesium.
- **LFTs:** These include total protein, albumin, total bilirubin (direct and indirect), alkaline phosphatase, AST (SGOT), ALT (SGPT)
- **Thyroid Function Tests:** TSH, T3, free T4
- **Coagulation Tests:** These include PT/INR, aPTT, D-Dimer and fibrinogen
- **LDH, Uric acid & phosphorus:** These along with serum chemistries and coagulation labs comprise tumor lysis labs

Concomitant Medications: Review (see section 4.4.6)

Tissue Acquisition/Disease Assessment: Primary tumor will be collected by peripheral blood and bone marrow biopsy. Buccal cell collection will be collected. Bone marrow biopsy and blood sample should be obtained within 14 days prior to day 1 of HiDAC. See section 6.7 and the laboratory manual for additional details.

6.3 Treatment Assessments-INDUCTION CYCLE (CYCLE 1)

6.3.1 Daily (or twice daily* as noted), D1-5 (High Dose Cytarabine administration)

Clinical evaluation: physical examination and ECOG performance status day 1 only, focused history on symptoms/toxicity days 1-5.

Laboratory studies:

- **CBC with differential and platelets**
- **Serum Chemistries*:** **twice daily:** sodium, potassium, chloride, bicarbonate, BUN, serum creatinine, glucose, calcium, magnesium.
- **LFTs:** **total protein, albumin,** bilirubin (direct and indirect), alkaline phosphatase, AST, ALT
- **LDH, Uric acid, phosphate*:** **twice daily**
- **Coagulation Tests:** PT/INR/aPTT, D-Dimer, fibrinogen

Concomitant Medications: Review

Toxicity Assessment: via NCI CTCAEv4

